10. STUDY ASSESSMENTS

Clinical Assessments will be done at baseline post crown placement; at months 3, 6, 12 and 18; and end of study visit occurring in range of 24 to 30 months from baseline.

Assessments and documentation required at each assessment interval:

• Photographs of selected teeth	Baseline
• Photographs of tooth preparations	Baseline and when possible
• Photographs of cemented crowns	Baseline
• Photographs of occlusal and frontal views	Baseline and when possible
• Assessment of fit	All intervals
• Assessment of positioning	All intervals
• Assessment of proximal contact	All intervals
• Assessment of marginal adaptation	All intervals
• Assessment of color: match , staining/color change	All intervals
• Assessment of time placement	Baseline
• Assessment of gingival status	All intervals
• Assessment of retention	3, 6, 12, 18 and 24 mo
• Assessment of veneer/composite integrity	3, 6, 12, 18 and 24 mo
• Assessment of secondary caries	3, 6, 12, 18 and 24 mo
• Assessment of trauma	3, 6, 12, 18 and 24 mo
• Assessment of clinical pulp pathology	3, 6, 12, 18 and 24 mo
• Assessment of radiographic pulp pathology	24 mo
• Assessment of tooth	All intervals
• Assessment of parents' esthetic satisfaction	All intervals (baseline at 3-month follow up)

Non-recall assessment to be done at the time of tooth/crown lost to study due to trauma. If this was to occur, the patient would be discontinued from study and the justification recorded.

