11.0 DATA ANALYSIS

Descriptive statistics (means, standard deviations, counts, and percentages) will be calculated for all variables. To evaluate if the primary efficacy variables differ by the three treatment groups (NuSmile PVSCC Signature Crowns, NuSmile ZR, and Strip composite crowns), ANOVA or Chi-square tests of association will be performed.

All subjects evaluated at the 6-month interval or beyond and subjects who have lost crowns or teeth will be considered for efficacy. All enrolled subjects defined here as those who have had at least one crown placed will be evaluated for safety. Any missing, unused or false data will be omitted from data analysis.

The primary efficacy variables in this trial are fit, positioning, proximal contact, marginal adaptation, color match, gingival status, crown retention, veneer/composite integrity, secondary caries, occlusal integrity, history of trauma, clinical pulp pathology, parents' esthetic satisfaction. Scores for efficacy variables will be summarized and displayed using descriptive statistics (means, standard deviations, counts, and percentages).

Inferential statistics will be used to detect significant differences in the primary efficacy variables by the treatment status at baseline and at 6, 12, 18, and 24 month follow-up. Statistical differences will be calculated using logistic regression models accounting for within cluster variance using generalized estimating equations (GEE).

Safety variables include Adverse Events and Unanticipated Adverse Device Effects. All subjects that have had crowns placed will be evaluated for safety. Descriptions of occurrences, incidence, severity and required treatments for Adverse Events and Unanticipated Adverse Device Effects Will be summarized and tabulated where appropriate.

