APPENDIX 8: RETENTION

RETENTION	
A=	Intact
B=	Partially missing
C1=	Missing – no cement remaining on tooth or crown
C2=	Missing – some or all cement remaining on tooth
C3=	Missing – some or all cement remaining on crown interior (if crown available)
C4=	Missing – some cement remaining on both tooth and crown interior (if crown available)

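### Missing data are omitted and no rule says how a failed crown, or a child discontinued after trauma, counts at later visits, so 24-month failure may be biased in either direction

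*Combined protocol and SAP*

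**What the plan says.** Four rules bear on this point.

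- **Omission (Section 11.0).** "Any missing, unused or false data will be omitted from data analysis". The plan has no imputation, no carry-forward of failure, no time-to-event analysis and no sensitivity analysis.
- **Comparison times (Section 11.0).** The primary efficacy variables are tested "by the treatment status at baseline and at 6, 12, 18, and 24 month follow-up", using logistic GEE to allow for clustering. Whether this means one model per visit or one longitudinal model is not stated.
- **Efficacy set (Section 11.0).** "All subjects evaluated at the 6-month interval or beyond and subjects who have lost crowns or teeth will be considered for efficacy".
- **Trauma loss (Section 10).** "Non-recall assessment to be done at the time of tooth/crown lost to study due to trauma"; after that, "the patient would be discontinued from study and the justification recorded". The rule acts on the child, who may have up to four crowns (Section 6).

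Retention is scheduled at 3, 6, 12, 18 and 24 months (Section 10). Appendix 8 gives a lost crown its own codes, C1 to C4, for example "Missing – no cement remaining on tooth or crown". Retention and history of trauma are both on the Section 11.0 list of primary efficacy variables.

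**The concern.** Loss of a crown persists: a crown lost at month 5 is still a failure at month 24. A 24-month comparison therefore needs a rule for failures recorded earlier, and the plan has none. For trauma losses the gap is built in. An outcome event ends follow-up, later scores do not exist, and the omission sentence removes the child from later comparisons. The child's other crowns go too, whether or not they had failed. Unweighted GEE on the data that remain is generally valid only if missingness is unrelated to outcome, and here a stated rule relates them.

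The non-recall assessment does not close the gap, because it is assigned to none of the listed comparison times. A child discontinued for trauma before month 6 belongs to the efficacy set but has no score at any listed post-baseline comparison.

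The efficacy set adds a selection of opposite sign. A child with an early loss is kept; a child with intact crowns who is never evaluated at month 6 or beyond is dropped.

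At stake are the later failure rates and arm comparisons. Clinical performance is the stated objective (Section 3), and there are only 30 children per arm (Section 5), so the handling of a few failures matters.

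**Working it through.** **What the plan's figures allow.** The sample size is a convenience number; 3 × 30 = 90 agrees. Planned crowns are 120 to 200, so 120/90 = 1.33 to 200/90 = 2.22 per child. No failure or dropout rate is given, so there is no plan figure to reproduce. Everything below is an illustration on assumed rates.

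**Assumptions.** Constant failure hazard; true 24-month cumulative failure F of 10% to 40%; crowns treated as independent, so clustering and the loss of a discontinued child's other crowns are ignored.

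**Failures by month 18.** F18 = 1 − (1 − F)^(18/24). For F = 20%: 1 − 0.8^0.75 = 0.1541.

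**Case A: a share t of failures up to month 18 is absent from the 24-month table.** Shown rate = (F − t·F18)/(1 − t·F18). For F = 20%:

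- t = 10%: 0.18459/0.98459 = 0.18748, or 18.7%
- t = 25%: 0.16147/0.96147 = 16.8%
- t = 50%: 0.12295/0.92295 = 13.3%
- t = 100%: 1 − 0.8^0.25 = 5.4%

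**Case B: known failures are kept, unfailed dropouts are omitted.** Dropout is independent of failure, with constant hazard and 24-month probability d. Let a = −ln(1 − F) and b = −ln(1 − d). Known failures K = a/(a + b) × [1 − (1 − F)(1 − d)]; shown rate = K/[K + (1 − F)(1 − d)]. For F = 20%:

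- d = 10%: 0.1902/(0.1902 + 0.72) = 20.9%
- d = 20%: 0.18/(0.18 + 0.64) = 22.0%
- d = 30%: 0.1693/(0.1693 + 0.56) = 23.2%

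**Range over F (shown 24-month failure, %).**

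| Handling | F = 10 | F = 20 | F = 30 | F = 40 |
|---|---|---|---|---|
| A, t = 10% | 9.3 | 18.7 | 28.3 | 38.0 |
| A, t = 25% | 8.3 | 16.8 | 25.6 | 34.8 |
| A, t = 50% | 6.4 | 13.3 | 20.7 | 28.6 |
| A, t = 100% | 2.6 | 5.4 | 8.5 | 12.0 |
| B, d = 10% | 10.5 | 20.9 | 31.2 | 41.4 |
| B, d = 20% | 11.1 | 22.0 | 32.6 | 43.0 |
| B, d = 30% | 11.8 | 23.2 | 34.2 | 44.8 |

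**Between arms.** Under full omission, a true 20% versus 40% appears as 5.4% versus 12.0%, a difference of 6.6 points instead of 20. It shrinks but does not reverse.

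Case B also shows that carrying failures forward is not enough while unfailed dropouts are still omitted.

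**The case against.** The strongest answer is that the plan does not discard failures. The efficacy set expressly keeps children who have lost crowns or teeth, and Appendix 8 makes a lost crown a scored outcome. Only trauma loss triggers discontinuation. A child with secondary caries, pulp pathology or a crown lost for another reason has later visits scheduled and can be scored again. The withdrawal reasons in Section 12.2 do not include crown failure, caries or pulp pathology. A child first seen again at month 12 stays in the efficacy set. Variables such as fit, color and marginal adaptation can be scored only on a crown in place, so restricting them to retained crowns is inherent.

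All of this stands, and it limits the point. A reader might infer that early failures in general vanish from later visits, that 24-month failure is therefore certainly understated, and that 20% would be reported as about 5%. The documents do not support that. Omission at each visit separately is itself an inference from the listed comparison times. The 5.4% needs every failure up to month 18 to be left out, whereas the explicit rule reaches trauma losses only. The efficacy set pushes the rate upward.

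What the answer does not do is supply the missing rule. Being considered for efficacy creates no month-24 score, and a C code recorded once is nowhere said to count at month 24.

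**Conclusion.** The point holds as a gap with a built-in source of bias. After a trauma loss, the discontinuation and omission rules together make a primary outcome event the cause of missing later scores. For other failures, the plan does not say how they count later. Failure is understated if earlier failures are left out, and overstated if they are kept while unfailed dropouts are omitted. For an assumed true 20%, the shown figure runs from 13.3% (half of the earlier failures omitted) to 23.2% (failures kept, 30% dropout), with 5.4% as an extreme bound. These figures rest on a constant hazard and independent crowns, and on rates the documents do not give.

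A reader might also infer that the arm with more early failures would overtake its comparator. The constant-hazard calculation shows the difference compressed, not reversed.

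This should be fixed before analysis, because the same text permits materially different 24-month results.

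**What to change.** 1. Replace the omission sentence. A recorded crown failure (retention C1 to C4, or another failure defined in advance as irreversible) counts as failed at every later analysis time, including failures recorded at the non-recall assessment.
2. Analyse retention and other irreversible failures as time from placement to first failure, with child-clustered variance. Treat natural exfoliation as a separate competing or censoring event, not as failure: Section 6.2 excludes only teeth expected to be lost within one year, while the final visit falls at 24 to 30 months (Section 8).
3. Analyse variables that need a crown in place as conditional on retention, and label them so.
4. Include all randomised children with a crown placed, and add a sensitivity analysis for crowns not seen.
5. Reconcile the discontinuation sentence in Section 10 with the efficacy-set and omission sentences in Section 11.0.

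The cost is SAP wording and programming, with no new data. Some failure rates may look less favourable.

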8. CLINICAL ASSESSMENTS

Clinical Assessments for both groups will be done at post crown placement (baseline); and months 3, 6, 12, and 18; and end of study visit occurring in range of 24 to 30 months from baseline. Please see Appendix 3 for scoring Criteria for the following:

- Fit
- Positioning
- Proximal Contact
- Marginal Adaptation
- Color: Match, staining/color change
- Gingival Status
- Retention of the crown
- Integrity of the veneer/composite
- Secondary Caries
- History of trauma
- Clinical pulp pathology
- Radiographical pulp pathology
- Parents' esthetic satisfaction

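### Thirteen unranked primary variables are tested at five times with no primary variable or time, no alpha, no error control and no exploratory label, and the list does not match what is scheduled and scored

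*Combined protocol and SAP*

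**What the plan says.** Section 11.0 lists 13 variables without ranking. The list opens "The primary efficacy variables in this trial are fit, positioning, proximal contact, marginal adaptation, color match, gingival status, crown retention", continues with veneer/composite integrity, then "secondary caries, occlusal integrity, history of trauma, clinical pulp pathology", and closes with parents' esthetic satisfaction.

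On testing it says "Inferential statistics will be used to detect significant differences in the primary efficacy variables". The arms are to be compared at five times, in the plan's words "by the treatment status at baseline and at 6, 12, 18, and 24 month follow-up". ANOVA or chi-square tests across the three groups are named first. Later in the section, "Statistical differences will be calculated using logistic regression models accounting for within cluster variance", by GEE. The section does not say whether each comparison is one overall test or a set of pairwise contrasts, or whether visits are tested separately or in one model per variable. On gaps in the data: "Any missing, unused or false data will be omitted from data analysis".

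Sections 2 to 5 call the study a pilot, and Section 5 describes 90 subjects (30 per arm) as a convenience sample. Section 11.0 does not refer to pilot status.

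On timing, Section 8 says "Clinical Assessments for both groups will be done at post crown placement (baseline") and at later visits, followed by one general list. Section 10 gives an item-by-item schedule. It starts five of the primary variables at month 3, and for parents' satisfaction it reads "All intervals (baseline at 3-month follow up").

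**The concern.** When 13 variables are equally primary at several times, any of them at any visit could be reported as the primary result. If nothing limits the tests, the chance of at least one false positive is well above the per-test level, and a reader of the results cannot tell a planned finding from a selected one.

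The analyst would also meet practical gaps: a primary variable with no scale under its name, baseline tests that may have no data, a baseline that is really a month-3 score, and an integrity scale that does not say how to score one of the three arms.

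**Working it through.** **The plan's own figure.** 3 arms × 30 = 90, which agrees with Section 5. The plan gives no power calculation, alpha or error rate to reproduce.

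**Counting the tests.**
- As written in Section 11.0: 13 variables × 5 times = 65.
- Occlusal integrity has no scale or scheduled assessment under that name: 65 − 5 = 60.
- Section 10 gives no baseline score for retention, veneer/composite integrity, secondary caries, trauma and clinical pulp pathology: 60 − 5 = 55.
- If the month-3 satisfaction score is not counted as baseline: 55 − 1 = 54.
- Check: 6 variables × 5 times + 5 × 4 + satisfaction at 5 or 4 times = 55 or 54.

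**Chance of at least one false positive.** Assumptions: alpha 0.05 per test (none is stated), no true differences, and each test having exactly its nominal size. For k independent tests the chance is 1 − 0.95^k:
- k = 12 (one time, without occlusal integrity): 1 − 0.95^12 = 46%
- k = 13: 1 − 0.95^13 = 49%
- k = 54 or 55: 94%, with 0.05 × 54 = 2.70 or 0.05 × 55 = 2.75 false positives expected

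The variables and visits are correlated, so independence is an upper reference. Simulated test statistics (60,000 sets) for 12 variables at a single time give:

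| Assumed correlation between variables | One overall test each (2 df) | Three unadjusted pairwise contrasts each |
|---|---|---|
| 0 | 46% | 79% |
| 0.5 | 33% | 61% |
| 0.9 | 14% | 30% |

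For 12 variables × 4 follow-up visits = 48 overall tests, the chance falls from 85% (assumed correlation 0.2 between variables, 0.5 between visits) through 60% (0.5, 0.8) to 24% (0.9, 0.9).

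**The list set against the schedule and scales.**
- *Occlusal integrity* appears only in Section 11.0. It is absent from the Section 8 list, the Section 10 schedule and the appendices. Appendix 2 (positioning) does score whether a tooth is in occlusion, and Section 10 schedules an assessment of the tooth that has no scale.
- *Five variables at baseline.* Section 10 starts them at month 3. Section 8 can be read as scoring everything at baseline. Neither section says which governs.
- *Satisfaction.* Its baseline is taken at month 3, which is not one of the Section 11.0 test times.
- *Integrity.* Appendix 9 grades loss of veneer or composite. Section 1 describes the ZR crown as monolithic zirconia, and no rule says how it is scored. If every ZR crown is scored intact, there are no ZR events and a logistic model has no finite ZR odds ratio. If ZR is left blank, the omission of missing data removes the arm.

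**The case against.** The strongest defence is that this is a pilot with a convenience sample, where formal error control is not expected. That would fully excuse a plan limited to estimation, or one that called its p-values exploratory. Section 11.0 does neither: it seeks significant differences in variables it calls primary. Pilot status makes the matter less grave and keeps the remedy small, but it does not supply the missing limit.

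A second defence is that the size rests on assumptions. This is true. Alpha and the correlations are not in the documents, and the range is wide. Tests of rare events also fall below nominal size: a three-arm chi-square test with 30 children per arm has a true size of about 0.6%, 2.0% and 3.6% at assumed event rates of 1%, 2% and 5%. A simulation of the planned logistic GEE that allows for this, with assumed event rates and clustering, still gives 22% to 42% for 12 overall tests at one time.

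Four stronger readings are tempting, and the documents do not support them.
- *A false positive is nearly certain.* The 94% figure needs 54 or 55 separate, independent tests, and the plan does not say that visits are tested separately.
- *The risk passes 50% only if visits are tested separately.* This holds for overall tests but not for unadjusted pairwise contrasts, which give 61% to 79% at one time for correlations of 0.5 to 0.
- *The five baseline tests cannot be run, and occlusal integrity is not collected.* Section 8 allows baseline scoring of the five, and occlusal integrity may be an existing item under another name.
- *Scoring ZR crowns as intact is an artefact.* It may reflect a real product difference. Section 7.5.3 also recognises fracture of a ZR crown, so the scale could be adapted. The fault is the absence of a rule.

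**Conclusion.** The concern holds. The plan has 13 co-equal primary variables, 65 tests as written and 54 or 55 that Section 10 supports, with nothing to rank, limit or label them. At an assumed alpha of 0.05 and nominal test size, the chance of at least one false positive at a single time is 14% to 46% with overall tests and 30% to 79% with unadjusted pairwise contrasts. Separate testing of visits raises it further. Every setting examined exceeds 5%, but the documents do not fix one figure within these ranges.

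The mismatches between list, schedule and scales rest on the text alone and stand whatever view is taken of multiplicity. None of this invalidates a pilot. It should be corrected before analysis because it decides what may be claimed from the results.

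**What to change.** Before analysis:

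1. Choose one of two routes; the choice is the sponsor's.
   - State that all p-values are exploratory, and base conclusions on estimates with confidence intervals that account for clustering by child. This is the smaller change and suits a pilot.
   - Or name one primary variable at one time, with two contrasts against strip crowns under Holm or Dunnett, and label everything else exploratory.
2. Define occlusal integrity by an existing scored item, or remove it from the primary list.
3. Reconcile Sections 8 and 10, and drop baseline tests for any variable not scored at baseline.
4. Label the first satisfaction score as month 3.
5. State how ZR crowns are scored on the integrity scale. If the scale does not apply to them, limit that comparison to Signature versus strip crowns. Report teeth that received a composite crown instead (Section 7.5.4) the same way in both preformed-crown arms.

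The cost is wording in Sections 8, 10 and 11.0 and one scoring rule, with no extra subjects or visits. The downside is that variables not named as primary can no longer support confirmatory claims. If ZR is ruled not applicable, that arm has no result on the integrity scale.

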5. SAMPLE SIZE

As this is a pilot study, a sample size of 90 (30 in each arm) subjects will be chosen as a convenience sample. This is the number estimated to enroll in a 24 week period.

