6. STUDY POPULATION

Ninety (90) subjects contributing to approximately 120 to 200 crowns on primary teeth will be recruited from the patient pool of the Center for Pediatric Dentistry who receive care under general anesthesia and enrolled into the study. A maximum of four crowns will be placed in any subject. It is estimated that it will take approximately 24 weeks to place all crowns and complete the baseline examination.

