7.4 Treatment Randomization

Restorations will be randomly allocated to a patient; all teeth in a single patient will be randomly allocated to receive one of the restoration treatments: 1) NuSmile Signature crowns (thirty patients in the intervention group 2) NuSmile ZR crowns (thirty patients in the intervention group and 3) and composite strip crowns (thirty patients in control group).

The randomization sequence will be created using STATA 12.0 (StataCorp, College Station, TX) statistical software using random block sizes, which are known only to the study statistician. The randomization list will be created and placed in the order determined above into opaque sealed envelopes prior to trial start. The envelopes will be kept in a secure place known only to the study coordinator, research assistants, and statistician.

Each patient will be assigned a random treatment when they arrive at the treatment appointment and after they have been determined eligible and have signed the consent form. The clinician will be told the treatment assignment immediately prior to the treatment appointment.

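### The planned logistic GEE has no fallback for sparse Absent/Present outcomes, where an arm without events gives no finite odds ratio and the Wald test rarely rejects

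*Combined protocol and SAP*

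**What the plan says.** Section 11.0 names 13 primary efficacy variables and plans inference at baseline and at 6, 12, 18 and 24 months. Its model is logistic regression, "accounting for within cluster variance using generalized estimating equations (GEE". The section names no variance estimator, working correlation, small-sample correction or reference distribution, and has no rule for an arm without events. It also plans descriptive counts and percentages, and ANOVA or chi-square tests.

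Three of the 13 variables are scored only as Absent or Present: secondary caries (Appendix 10), trauma (Appendix 11) and clinical pulp pathology (Appendix 12).

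The child is the unit of allocation. Section 7.4 says that "all teeth in a single patient will be randomly allocated to receive one of the restoration treatments". Section 5 says that "a sample size of 90 (30 in each arm) subjects will be chosen as a convenience sample". Section 6 expects "Ninety (90) subjects contributing to approximately 120 to 200 crowns on primary teeth" and adds: "A maximum of four crowns will be placed in any subject". On incomplete data, section 11.0 says: "Any missing, unused or false data will be omitted from data analysis".

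**The concern.** A logistic model estimates log odds. If no crown in an arm has the event, that arm's estimated log odds is minus infinity, and any odds ratio against it is zero or infinite. GEE changes the standard error but does not remove this. When an arm has only one or two events, the estimate exists, but its standard error is so large that the Wald statistic can hardly reach significance.

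The clearest result a small trial could show, such as no secondary caries in one arm and several cases in another, is therefore the one that the planned model cannot report. With no fallback stated, the analyst would have to choose a rescue method after seeing which arm has no events.

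**Working it through.** **Inputs from the documents.** 30 children in each of 3 arms (sections 5 and 7.4). Crowns per child: 120/90 = 1.33 to 200/90 = 2.22, at most 4 (section 6). Crowns per arm: 120/3 = 40 to 200/3 = 66.7. The figure of 90 is a convenience number, so no power calculation exists to reproduce; only 3 × 30 = 90 can be checked.

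**Assumptions.** Event rates of 2%, 5% and 10% per crown (sparse) and 20-40% (common); within-child correlation of 0.3 to 0.6; 30 evaluable children per arm; two-sided 5% level. The documents state none of these.

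**Step 1: closed-form bounds on an arm with no events.** If an arm holds N independent observations with event rate p, the chance that at least one of three arms has no events is 1 − (1 − (1−p)^N)^3. Taking crowns as fully independent (N = 66.7 at the most crowns) gives a lower bound. Taking each child as a single observation (N = 30) gives an upper bound. At p = 5%:

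- N = 66.7: 0.95^66.7 = 0.033, giving 1 − 0.967^3 = 9.5%.
- N = 40 (fewest crowns, independent): 0.95^40 = 0.129, giving 1 − 0.871^3 = 34%.
- N = 30: 0.95^30 = 0.215, giving 1 − 0.785^3 = 52%.

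**Step 2: simulation with correlated crowns.** Beta-binomial data, 1 to 4 crowns per child with means from 1.33 to 2.22, correlation 0.3 and 0.6, 40,000 data sets per setting. The table gives the share of trials with no finite estimate in at least one arm, at 30 per arm. The bounds use N = 66.7 and N = 30.

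| Event rate per crown | Simulated | Closed-form bounds |
|---|---|---|
| 2% | 72-88% | 59-91% |
| 5% | 19-45% | 9.5-52% |
| 10% | 1-9% | 0.3-12% |

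Each simulated range lies inside its bounds. If loss to follow-up left 20 children per arm, the 5% figure would rise to 42-68%; at 15 it would be 60-81%. Both losses are assumptions.

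**Step 3: error rate when estimates exist.** At 5% events and 30 per arm, the 2-df robust Wald test rejects about 0.3-1.8% of null trials. A hand example with one crown per child, where the robust and ordinary variances coincide, shows why:

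- 6 of 30 children against 1 of 30: log odds ratio = ln[(6/24)/(1/29)] = 1.98. Standard error = √(1/6 + 1/24 + 1/1 + 1/29) = 1.11. z = 1.78, not significant. The single event contributes 1 of the 1.24 variance units.
- 6 of 30 against 0 of 30: no finite odds ratio. The exact two-sided p-value from reassigning labels is 2 × C(30,6)/C(60,6) = 2 × 593,775/50,063,860 = 0.024.

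The permutation argument thus finds evidence where the planned model returns nothing.

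**Step 4: the alternative.** In simulation, a permutation test of arm labels across children held its size at 4.4-5.2% for event rates of 2-5%. In scenarios with true differences it rejected in 75-92% of trials, and the GEE Wald test in 0-70%. Those differences come from no figure in the documents, so the percentages show the gap between methods, not this trial's power.

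**Step 5: common outcomes.** At 20-40% events and 30 per arm, the usual robust 2-df test rejects about 4.6-6.4% of null trials across 1.33 to 2.22 crowns per child. It falls below nominal at 20% events and 1.33 crowns. With an exchangeable working correlation and a true correlation of 0.6, pairwise tests at 30-50% events are at 4.9-5.2%.

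**The case against.** **The plan does not name the robust variance.** This is correct. A reader might infer that the GEE analysis is too liberal for common outcomes, because sandwich variances need many clusters. The documents do not support that as a finding. A bias-corrected GEE would comply with section 11.0, and even the ordinary robust version is within about 1.4 points of nominal at 30 per arm, sometimes below it. The separation problem is different: it arises whichever variance estimator is used.

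**No event rates are given, so the outcomes may not be rare.** This also stands. At 10% events and 30 per arm only 1-9% of trials are affected. The point is conditional, but the plan cannot exclude the sparse case, and three of its primary variables are simple Absent/Present items.

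**Some results would still be available.** A reader might infer that the affected comparisons give no result at all. That goes too far: the counts, percentages and chi-square tests in section 11.0 can be computed with an empty arm. What fails is the model that the section relies on to account for clustering.

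**Attrition.** Omitting missing data reduces the number of children, but no dropout rate is stated. Figures at 15 or 20 per arm only illustrate sensitivity.

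**This is a pilot with a convenience sample.** That limits how much weight any test can bear. Yet section 11.0 commits to detecting significant differences in primary variables, and small samples are where this method fails.

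**The threshold for switching methods.** A limit of 5 children with events is a convention, and the switching rule as a whole has not been simulated. This stands.

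**Conclusion.** The concern holds for sparse binary outcomes. With 30 children per arm, the planned logistic GEE has no finite odds ratio for at least one arm in about 19-45% of trials at 5% events and 72-88% at 2%. Where it does give estimates at 5% events, its joint Wald test runs at about 0.3-1.8% instead of 5%. These figures rest on assumed event rates, a correlation of 0.3-0.6 and no loss of children. More loss makes them worse; event rates of 10% or above largely remove the problem of empty arms.

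For common outcomes the test is close to nominal, and any departure is minor and depends on crowns per child and the working correlation. The point is of modest weight overall, but the remedy replaces a stated method that can fail with one that works, at almost no cost.

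**What to change.** Add to section 11.0:

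1. For any binary outcome with few children having the event in any arm (for example fewer than 5, stated as a convention), replace the GEE Wald test with a permutation test. It reassigns arm labels across children, never across single crowns, and follows the randomisation, including its blocks.
2. For those outcomes, report Firth-penalised odds ratios with the number of children with the event in each arm. Fitting them at child level avoids treating crowns in one mouth as independent.
3. For other outcomes, name the working correlation and variance estimator. Optionally, use a Kauermann-Carroll type corrected sandwich with an F reference. At 30 per arm, about 1.8 crowns per child and a correlation of 0.3, its joint size is 4.4-4.6% at 20-50% events. Mancl-DeRouen is not a good substitute: it overcorrects here, to about 3.6-4.4% at 30 per arm.

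A variance correction alone does not cure an empty arm, so item 3 cannot replace items 1 and 2.

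The cost is some SAP text and a little more analysis work, plus slightly wider intervals for common outcomes if the correction is used. No extra children, visits or data are needed.
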